A limiting factor in the use of epidural analgesia, however, is the high incidence of associated hypotension. Hypotension is defined as systolic blood pressure (SBP) > 20% below the baseline preoperative measurements and acquired before the epidural or any sedation has been administered. Effective segmental epidural block would thus invariably cause sympathectomy due to its location in the thoracic or lumbar areas by blocking the cardiac sympathetic nerves, the pre-ganglionic nerves to the adrenal glands or the sympathetic nerves to the blood vessels individually or in combination.

It has been proven beyond doubt that epinephrine, when added to ropivacaine 0.2% and used for epidural analgesia by infusion, is safe and may even improve spinal cord blood flow and the analgesic effects of ropivacaine.⁷ It is also known that the cause of hypotension associated with epidural analgesia is the blockade of the sympathetic outflow to the cardiovascular and adrenal systems, and that the ideal mechanism to counter this would be by beta1-stimulation, which is ideally achieved with low-dose epinephrine.

Finally, it is known that epidural infused epinephrine increases its serum concentration.⁸ What is not known is whether added epinephrine will counteract this sympathetic blockade and prevent hypotension, and what the optimal concentration of epinephrine infusion would be during epidural analgesia with 0.2% ropivacaine to achieve optimal analgesia and optimal hemodynamic status.

5. Specific Aims:

We aim to examine whether adding epinephrine will counteract the sympathetic blockade and prevent hypotension, and what the optimal concentration of epinephrine infusion would be during epidural analgesia with 0.2% ropivacaine that can achieve both optimal analgesia and optimal hemodynamics. Specifically we plan to answer the following questions:

- 1. Does the addition of epinephrine to the epidural infusion of 0.2% ropivacaine:
 - a. Prevent hypotension?
 - b. Lead to a wider spread of local anesthetic effect?
 - c. Lead to a difference in the average pain scores?
 - d. Lead to a difference in when ambulation occurs?
 - e. Decrease potential of other opioid-related side effects such as pruritus, nausea/vomiting, respiratory depression and opioid consumption?
- 2. What is the optimal concentration of epinephrine (2mcg/mL or 5mcg/mL) to achieving the above-mentioned outcomes?

6. Research Plan:

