- The epidural infusion will be continued intraoperatively at a rate 4 to 8 mL per hour. Emergence medications will be administered and recorded as judged appropriate by the intraoperative anesthesiologist. A bolus of 5 mL of ropivacaine 0.5% without additives may be administered through the epidural catheter at the conclusion of the intraoperative phase by the intraoperative anesthesiologist or APS anesthesiologist in the recovery room, if required.
- "Rescue" drugs as outlined below will be administered and recorded if deemed necessary. If, after sensation level testing, the epidural block was not appropriately covering the area of surgery, a further bolus of 5 mL of 0.5% ropivacaine will be injected by the APS physician and if this was still not managing the pain, this will be noted and the patient will be removed from the study. If judged appropriate by the APS physician, the epidural will either be replaced in the recovery area or the "rescue" medication described below will be initiated.
- Hypotension is defined as SBP > 20% below the baseline in the block room area before the epidural or sedation for the epidural was administered or an MAP less than 55 mmHg. Epidurals will be turned down or turned off if the treating Intensive Care Primary Physician declared it an emergency, if the patient had hemodynamic instability stemming from other causes that was complicated by the sympathetic block of the epidural, or significant hypotension, or mean MAP <

30%, from baseline and other causes such as hypovolemia had been corrected. If this is the case, the patient will be removed from the study.

Research-Related Procedures - Postoperative Periods:

If additional pain management or "rescue" analgesics are needed, for example, from outside the area covered by the epidural; subjects may receive any of the following:

- Acetaminophen (Tylenol) 1000 mg scheduled intravenously every 8 hours for the first 48 hours and, after oral intake is restarted, it will be changed to 1 gram every 6 hours by mouth (patients with liver disease will be excluded if appropriate and after discussion with the hepatic surgeon)
- Ketorolac Tromethamine (Toradol) 30 to 60 mg every 6 hours intravenously
- Celecoxib (Celebrex) 100 mg per mouth every 12 hours
- Oxycodone 5 to 10 mg per mouth every 4 hours as needed
- Intravenous hydromorphone (Dilaudid) patient-controlled analgesia (PCA) as per APS routine protocol appropriate for age and body habitus of the patient.

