Primary measurements:

Include the average invasively or non-invasively measured SBP, diastolic blood pressure (DBP), MAP, arterial blood oxygen saturation (SaO2), heart rate, respiratory rate, and pain by the visual analog pain score (VAS) on the "Defense and Veterans Pain Rating Scale" (DVPRS) measured over the following set periods:

Preoperative period

Primary measurements every 3 to 5 minutes and at indicated time points:

- I. Before the bolus epidural is injected.
- II. After the epidural bolus is injected but before anesthesia is induced.

Intraoperative period

Primary measurements every 3 to 5 minutes

Postoperative period

I. Primary measurements in the recovery room (if appropriate) every 15 minutes

II. Primary measurements following transfer to the floor every 4-6 hours if within normal limits, but every hour if needed for closer observation in case of possible abnormality for as long as the epidural analgesic blocks are continued, but at least every 8 hours after discharge from the PACU.

Secondary measurements:

[figure not shown]
- III. Spread of block per spinal root segment as tested by sensitivity to cold recorded every hour postoperatively and every 8 hours for the subsequent 72 hours after discharge from the PACU.
- IV. Ambulation on the first day after surgery (POD 1), POD 2 and 3, will be recorded per physical therapy protocol and distance ambulated per 24hour period will also be recorded. Physical Therapy information will be gathered to test motor effect on lumbar epidurals.
- V. Opioid usage data will be recorded and converted to morphine equivalents and averaged for POD 0, 1, 2, and 3 per group.
- VI. Side effects such as pruritus, nausea/vomiting, and respiratory depression (defined as respiratory rate less than 10 breaths per minute of oxygen saturation more than 7 points lower that the patients preoperative value on room air) will be recorded and managed as deemed appropriate by the attending physician.
- VII. 24 hour I/O for the first 72 hours to assess fluid balance, length of stay, and amount of days before return to PO status.

Data analysis plan

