All data will be entered securely using the online database or Red Cap. To assess potential dose-response effects on changes in continuously measured primary outcomes, repeated measures mixed modeling analyses will be used. This type of analysis can assess the main effects of time (i.e., change) and group (i.e., epinephrine dose; coded as an ordinal variable) on the outcomes. Mixed models are the preferred approach to analyze data with repeated measures; these models can account for correlation among repeated measurements, flexible time effects, and can handle missing data. Additionally, this model can estimate time × group interactions. If this interaction is statistically significant, that provides evidence that the changes in outcomes are different depending on the dose of epinephrine that a patient received. Logistic regression models will be used to assess the relationship between epinephrine dose and incidence of hypotension (SBP < 20% or MAP < 55 mmHg) and other categorical outcome variables. A P value of <0.05 was considered statistically significant for all statistical tests. All analyses were conducted in JMP Pro 11.0 (SAS Institute, Cary, NC).

Sample size determination

At 80% power (alpha = 0.05), a sample of n=200 (50 per group) will be able to detect 26% differences in incidence of categorical outcomes, and an effect size of Cohen's f = 0.24 for group mean differences and effect size of Cohen's f = 0.09 for group differences mean change over time. Figure 1 depicts how these effect sizes will translate to the outcomes, with assumed standard deviations in outcomes ranging from 5 to 25. For example, assuming MAP has an SD = 10, the present study will be able to detect mean differences of 5 mmHg across groups and group differences of 3 mmHg for mean change over time.

ADMINISTRATIVE RESPONSIBILITIES:

Study Resources: The principal investigator will oversee the data collection, data analysis and will maintain the records in confidence. Should any evidence suggest that the study protocol require modification, the PI will notify the IRB in a timely manner for review and approval. Each subject will be identified by number, not by name, on all data forms. To protect confidentiality, all data will be numerically coded and information linking the numeric codes to individual participant's names will be kept in a locked file in the PI's office.

7. Possible Discomforts and Risks:

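### Seven unranked primary measurements are each tested at 0.05, hypotension incidence is not named primary, and no 2 versus 5 mcg/mL comparison is planned for Aim 2

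*Combined protocol and SAP*

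**What the plan says.** Under Primary measurements the protocol lists what these "Include the average invasively or non-invasively measured SBP, diastolic blood pressure (DBP), MAP, arterial blood oxygen saturation (SaO2), heart rate, respiratory rate, and pain". That makes seven variables, to be recorded before, during and after surgery, with no order of importance and no single primary time window. The Data analysis plan calls the continuous ones primary outcomes and assigns them repeated-measures mixed models with time, group and time-by-group terms. Group is "epinephrine dose; coded as an ordinal variable".

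Logistic regression is planned for "incidence of hypotension (SBP < 20% or MAP < 55 mmHg" and for other categorical outcomes, without saying whether any is primary. The significance rule is "A P value of <0.05 was considered statistically significant for all statistical tests". There is no hierarchy, adjustment or gatekeeping.

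Preventing hypotension is in the title and is Aim 1a. Aim 2 (Specific Aims) asks: "What is the optimal concentration of epinephrine (2mcg/mL or 5mcg/mL) to achieving the above-mentioned outcomes". No analysis compares those two concentrations directly, and no rule says what makes one optimal.

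**The concern.** Three gaps act together.

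- **Multiplicity.** Seven primary results at 0.05 each give several chances of a positive trial when epinephrine does nothing. No rule says which result counts.
- **The main question is not the main endpoint.** SBP and MAP are primary, but the incidence of hypotension is not. A small shift in mean pressure could be reported as the primary success without showing that fewer patients became hypotensive, or the reverse.
- **Aim 2 has no test.** A significant dose effect, whether a trend or an overall test, says that dose groups differ somewhere. It can arise entirely from epinephrine versus none. With no 5 versus 2 mcg/mL contrast, a reader could take it as support for one dose over the other.

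**Working it through.** **Inputs from the documents.** Alpha 0.05 for every test; seven primary measurements; 50 per group; SD 10 and a 5 mmHg difference for MAP; a detectable difference of 26 points for categorical outcomes (Sample size determination). Correlations and hypotension rates are not given, so those below are assumptions. Tests are taken as two-sided. Group A is ropivacaine alone, B adds 2 mcg/mL and C adds 5 mcg/mL.

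**The plan's own figures.** One-way ANOVA with four groups, N = 200 and f = 0.24 has noncentrality 200 × 0.24² = 11.52 on 3 and 196 df, which gives 81.5% power; f = 0.24 reproduces. The 26 points reproduce at 50 per group if the lower rate is about 20% (20% v 46%: 79.9% power). At 24% v 50%, power is 78%.

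**Step 1: false-positive primaries.** With one group test per measurement and independence, 1 − 0.95⁷ = 0.302. Simulating seven equally correlated normal test statistics gives:

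| Assumed common correlation | At least one p < 0.05 |
|---|---|
| 0 | 30% |
| 0.3 | 27% |
| 0.5 | 23% |
| 0.7 | 18% |
| 0.9 | 11% |

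If the three pressures correlate at 0.85 and the rest at 0.2, it is 25%. Adding the hypotension test gives 1 − 0.95⁸ = 34% if independent. Reading both group and interaction for all seven gives up to 1 − 0.95¹⁴ = 51%.

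**Step 2: dose effect when the doses are equal, MAP.** Means 0/d/d, SD 10, 50 per arm, one time point. For d = 5:

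- Scores 0,1,2 (centred −1,0,1): contrast 5, standard error 10 × √(2/50) = 2, ratio 2.5, power 0.70.
- Scores 0,2,5: ratio 2.32, power 0.63.
- Overall F test: noncentrality 50 × 16.67/100 = 8.33, power 0.73.

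For d = 3 the three results are 0.32, 0.28 and 0.32. For d = 2 they are 0.17, 0.15 and 0.16.

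**Step 3: the same for hypotension.** Simulated score tests and 2-df chi-square, 50 per arm:

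| Assumed rates A/B/C | Trend 0,1,2 | Trend 0,2,5 | Overall | C v B alone |
|---|---|---|---|---|
| 50/24/24% | 0.79 | 0.74 | 0.82 | 0.05 |
| 50/35/35% | 0.34 | 0.30 | 0.34 | 0.05 |

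Only the direct comparison stays at its nominal level when the doses do not differ.

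**Step 4: error control for the pairwise tests.** With no true difference (all rates 50% or 30%, 50 per arm), three unadjusted pairwise tests give at least one significant result 12-14% of the time. Requiring a significant overall test first brings this to about 5%. Holm on B v A and C v A gives 4.0-4.6%.

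**Step 5: removed patients.** If hypotensive patients removed from the study were dropped from the analysis, a true rate p would be observed as p(1 − q)/(1 − pq), where q is the share of them removed. For 50% v 24%: q = 0.2 gives 44 v 20, q = 0.3 gives 41 v 18, and q = 0.5 gives 33 v 14. The difference falls from 26 points to 24, 23 and 20. Power at 0.05 falls from 0.78 to 0.71, 0.67 and 0.56. The values of q are assumed.

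**The case against.** The strongest reply is that an ordinal factor need not be a linear score. If its levels are kept, the planned model can yield the 2 versus 5 mcg/mL difference, and the 63-82% figures are correct rejections because epinephrine does work in those scenarios. That is true. What stands is that the plan names neither the contrast nor a decision rule, so nothing fixes how Aim 2 will be answered. Whether a reader would misread the dose effect is a risk, not a certainty.

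Second, the pressures are strongly related, so 30% overstates the error for seven tests. This is granted, and the table shows the range; every value exceeds 5%. In the other direction, the count omits the interaction and hypotension tests.

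Third, the MAP illustration uses one time point, not the planned repeated-measures model, so its percentages are indicative only.

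Fourth, hypotension leads the title and the aims, so its absence from the primary list may be a matter of labelling. A figure at the head of the secondary list is not shown in the text available, and hypotension could appear there. Neither point makes it primary.

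Fifth, a dose-finding study may report many outcomes as exploratory. It may, but this plan does not call them exploratory. It calls them primary and attaches a power statement and a significance threshold.

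Last, removal from the study need not mean that data already recorded are discarded. The plan does not say either way, which is why a rule is needed.

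**Conclusion.** The concern holds in all three parts. The false-positive chance across the seven primary measurements is 30% under independence and about 11-27% at assumed common correlations of 0.9 to 0.3, counting one test per measurement. A significant dose effect cannot by itself answer Aim 2. With equal doses and 50 per arm it appears 63-73% of the time for a 5 mmHg MAP shift with SD 10, and 74-82% at assumed rates 50/24/24%. It appears less often at smaller effects: 28-32% at 3 mmHg, 15-17% at 2 mmHg and 30-34% at 50/35/35%. The data would remain usable, but the headline result would be open to choice after the fact. The plan should be changed before analysis.

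**What to change.** 1. **Name one primary endpoint:** per-patient incidence of hypotension, over a stated window starting when the study infusion starts. First reconcile its definitions. Background has "Hypotension is defined as systolic blood pressure (SBP) > 20% below the baseline preoperative measurements"; the intraoperative section adds an alternative, "or sedation for the epidural was administered or an MAP less than 55 mmHg"; the Data analysis plan has "incidence of hypotension (SBP < 20% or MAP < 55 mmHg", which omits the reference to baseline. A ranked list of primaries with a stated multiplicity rule would also do.
2. **Analyse all randomised patients as allocated where data exist.** For those whose epidural is turned down or off, the intraoperative section says "If this is the case, the patient will be removed from the study". Where the reason is hypotension, count the patient as an event.
3. **Fit dose as a categorical factor** and pre-specify C v B with a 95% confidence interval. If there are exactly three arms, use an overall test followed by all three pairwise tests at 0.05. Otherwise use Holm on B v A and C v A, with C v B as key secondary. State whether optimal means hypotension alone or how the other Aim 1 outcomes enter.
4. **Make the seven measurements and the other outcomes secondary,** reported as estimates with confidence intervals.
5. **Restate the sample size** for this endpoint with an assumed control rate, once the number of arms is settled. The preoperative research section says both four and three groups, which is a separate conflict.

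**Cost.** No new procedures, but fewer confirmatory claims. The two columns show 50 per arm and 200 patients split over three arms (about 67 each):

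| Quantity (assumed rates) | 50 per arm | About 67 per arm |
|---|---|---|
| C v A power, unadjusted (50/24/24%) | 78% | 89% |
| C v A power, either method | 74% | 86% |
| Gated C v B power (50/35/20%) | 38% | 49% |
| C v B 95% CI half-width (rates near 30%) | 18 points | 16 points |

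The half-width is 1.96 × √(2 × 0.3 × 0.7/n). At the stricter Holm level and 50 per arm, the difference detectable with 80% power rises from about 27 to 29 points (control rate 50%) or from 22 to 24 (control rate 30%). The trial may not separate the two doses, and the report should say so.

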Patients will receive a bolus of 500 mL of 5% Albumin intravenous infusion as per the usual routine practice of the APS before the main bolus dose is injected. A preoperative level of block will be established that is appropriate for the surgery by injecting an appropriate volume of ropivacaine 0.5% or lidocaine 2% w/ epinephrine 1:200,000 (5–10 mL) into the epidural space as per the usual practice of the APS. This will be done after the routine test dosing with 3 mL of 2% lidocaine and 1:200,000 epinephrine, confirmed that intrathecal and intravascular markers are negative. If an insensate-to-cold area in the appropriate dermatomes cannot be established within 10 minutes following a 5 to 10 mL (maximum 10 mL) injection of ropivacaine 0.5%, the epidural catheter will be removed and replaced. If this process is repeated and there was still no level, it will be annotated and the patient will be removed from the study, labeled as a primary block failure, and treated appropriately by the attending anesthesiologist by either repeating the epidural block placement a third time or using other appropriate perioperative analgesia.

Research-Related Procedures - Preoperative Period:

Once consent is obtained, patients will be randomly allocated by computergenerated randomization to one of four groups. This will be a quintuple blinded prospective study. The anesthesiologist managing the intraoperative anesthesia, the anesthesiologists (APS) placing the blocks and following the patients on the floors, the research nurse taking the measurement, the surgeons, nor the patients will be aware of what combination of drugs are used for the epidural block infusion.

The three groups will consist of:

- 1. Group A (Ropivacaine 0.2% infusion; Control group)
- 2. Group B (Ropivacaine 0.2% + 2 mcg/mL epinephrine)

3. Group C (Ropivacaine 0.2% + 5 mcg/mL epinephrine)

The pharmacists will make up and supply test drugs for groups A, B and C and provide them labeled to the block area drug dispenser as "A, B, or C test solutions" without specifically identifying the content.

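### The randomisation text and the sample size describe four groups, but only three arms are defined and supplied, so the total, the number per arm and the power statement do not fit the trial.

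*Combined protocol and SAP*

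**What the plan says.** The section on research-related preoperative procedures says that "patients will be randomly allocated by computergenerated randomization to one of four groups". A few lines later it continues "The three groups will consist of" and lists A (ropivacaine alone, the control), B (with 2 mcg/mL epinephrine) and C (with 5 mcg/mL). Drug supply follows the list: "The pharmacists will make up and supply test drugs for groups A, B and C". The second specific aim asks "What is the optimal concentration of epinephrine (2mcg/mL or 5mcg/mL", which with the control also makes three arms. No fourth arm appears anywhere.

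The sample size section, at 80% power and alpha 0.05, says that "a sample of n=200 (50 per group) will be able to detect 26% differences in incidence of categorical outcomes". It adds Cohen's f = 0.24 for differences in group means and f = 0.09 for group differences in change over time. As an example, "assuming MAP has an SD = 10, the present study will be able to detect mean differences of 5 mmHg across groups". The data analysis plan uses repeated-measures mixed models with group entered as "epinephrine dose; coded as an ordinal variable", and logistic regression for hypotension.

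**The concern.** The number of arms, the allocation ratio and the total are the first facts that the statistician, the pharmacist and the ethics board need, and the protocol gives two incompatible versions. Four appears once as a word, in the randomisation sentence, and once as arithmetic, in the sample size. It is therefore not confined to a single typing slip.

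Two things are at stake. First, the power statement does not describe the three-arm trial. If the number per group is followed across the three supplied solutions, enrolment stops at 150 and power falls below the stated 80%. If the total is followed, power is higher than stated. Second, a randomisation list built from the four-group wording would send some patients to a code for which no solution exists. The list is not in the documents, so this is something to check and not a demonstrated error.

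**Working it through.** **Inputs.** From the sample size section: 80% power, alpha 0.05, N = 200, 50 per group, f = 0.24, a 26-point difference in incidence, and 5 mmHg at SD 10. From the arm list, drug supply and aims: k = 3. From the randomisation sentence: k = 4. The test behind f = 0.24 is not named; I assume a one-way ANOVA.

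**Step 1: the counts.** 200/50 = 4. With three equal arms, 3 × 50 = 150, or 200/3 = 66 to 67 per arm.

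**Step 2: the plan's own f.** For the omnibus F test on (k − 1, N − k) degrees of freedom, the noncentrality is λ = N f². At f = 0.24, λ = 200 × 0.0576 = 11.52, or 150 × 0.0576 = 8.64.

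| Design | λ at f = 0.24 | Power at f = 0.24 | Minimum f at 80% power |
|---|---|---|---|
| 4 arms, N = 200 | 11.52 | 81.5% | 0.236 |
| 3 arms, N = 200 | 11.52 | 86.4% | 0.221 |
| 3 arms, N = 150 | 8.64 | 74.3% | 0.256 |

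Only the four-arm design rounds to the stated 0.24. For three arms, f = 0.24 at 80% power needs N = 171 (57 per arm).

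**Step 3: the 26 points.** I read this as an unadjusted two-sided comparison of two arms (normal approximation, pooled variance under the null).

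- With 50 per arm, 20% v 46% has 79.9% power, so 26 points is reproduced at that rate. The detectable difference runs from about 20 points (lower rate 5%) to a maximum of 27.7.
- With 67 per arm, 20% v 46% has 90.2% power. The detectable difference from 20% is 22 points, and the maximum is 24.0.

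This figure depends on the number per arm and on a control rate that is not given. It does not identify the number of arms.

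**Step 4: the MAP example.** At SD 10, the range between the highest and lowest of three means that corresponds to the minimum f is:

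- one arm apart from two equal arms, range = f × 10 × 3/√2: 4.7 mmHg (N = 200) or 5.4 mmHg (N = 150);
- evenly spaced means, range = f × 10 × √6: 5.4 or 6.3 mmHg.

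If dose is instead tested as a one-degree-of-freedom linear trend with evenly spaced means, the detectable range is 4.9 or 5.6 mmHg, and a 5 mmHg range has 82% or 70% power. The plan gives neither the pattern of means nor the test, so 5 mmHg cannot be tied to one design.

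**Step 5: f = 0.09.** The number of repeats and their correlation are not given. With assumed values, four arms with N = 200 give 0.089 (4 repeats, correlation 0.6), and three arms with N = 200 give 0.090 (3 repeats, correlation 0.6). This figure does not discriminate.

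**The case against.** The contradiction itself is hard to dispute. The best case on the other side is that it does little harm.

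- **The arms are not really in doubt.** The aims, the arm list and the drug supply all agree on three, and the planned analysis runs on three arms as written. This stands, and it is why the group count should be corrected to three. It does not tell us the total.
- **The loss of power arises only at 150.** The inclusion criteria section expects 24 patients a month for 10 months (24 × 10 = 240) and would approach up to 250. Both sit closer to 200 than to 150, and at 200 power rises to 86%. This is fair, but neither figure is a stated analysis total.
- **f = 0.24 does not prove a four-arm calculation.** The plan analyses repeated measures, and three arms of 50 also give 0.240 under a repeated-measures between-group calculation with an assumed 2 repeats and correlation 0.75. This stands. The firm evidence is the randomisation sentence and 200 = 4 × 50.
- **The gain at 200 is conditional.** Patients can be removed after block failure or severe hypotension. If 200 were randomised and, as an assumed upper case, 20% were removed, 160 would remain. Three arms then have a minimum f of 0.248 and 77% power at f = 0.24. With an assumed Bonferroni correction for three pairwise comparisons, 20% v 46% at 67 per arm has 80% power, so the margin in Step 3 disappears. Both qualify how far the stated figures can be called conservative.

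**Conclusion.** The point holds and must be fixed. The stated size and power do not describe the three-arm trial that the protocol defines and supplies, and nothing elsewhere in the document resolves the conflict. At f = 0.24 the consequence ranges from a gain (86% power with 200 patients) to a shortfall (74% with 150), against the stated 80%.

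These percentages rest on a one-way ANOVA with equal arms and no loss of patients. The contradiction in the counts rests on no assumption. The missing control incidence, pattern of means and repeat correlation limit what can be verified, but they are separate gaps and add no weight to this conclusion.

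**What to change.** 1. Correct the group count in the randomisation sentence to three, to match the arms defined and supplied, and state the allocation ratio (1:1:1 if equal arms are intended, as a single number per group implies).
2. Check that the randomisation list has three codes. Regenerate it only if it has four.
3. State one total and one number per arm, and say whether it counts patients randomised or analysed. The sponsor must confirm which total was intended.
4. Restate the detectable effects for that design. With 200 in three arms: f = 0.22 and at most about 24 points pairwise. With 150: f = 0.26 and up to about 28 points pairwise.
5. While rewriting the paragraph, give the control incidence behind the categorical figure, and the pattern of means and the test behind the MAP figure. Recompute the change-over-time figure for three arms with its number of repeats and correlation.

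The cost is a protocol wording change, a check of the list and a recomputed power paragraph. Keeping 200 does not increase the sample size, and before any allowance for removals or multiple comparisons, f and the pairwise incidence difference become more favourable than stated.

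### The detectable effects are worked out for four groups of 50, not the three arms listed; the 26-point figure has no base rate, and 3 mmHg does not match the conversion behind 5 mmHg.

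*Combined protocol and SAP*

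**What the plan says.** The section 'Sample size determination' opens "At 80% power (alpha = 0.05") and bases its figures on "a sample of n=200 (50 per group"). It gives three detectable effects. The sample "will be able to detect 26% differences in incidence of categorical outcomes"; the other two are Cohen's f = 0.24 for group means, and f = 0.09 for change over time. For MAP with an SD of 10 it translates the two f values into 5 mmHg across groups and "group differences of 3 mmHg for mean change over time". It refers to a Figure 1 for the translation; that figure is not in the text available for this review.

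Under 'Research-Related Procedures - Preoperative Period', the randomisation sentence says "patients will be randomly allocated by computergenerated randomization to one of four groups". The list that follows is introduced by "The three groups will consist of" and names a control and two epinephrine concentrations (2 and 5 mcg/mL). No fourth arm is described.

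The 'Data analysis plan' says "Logistic regression models will be used to assess the relationship between epinephrine dose and incidence of hypotension", and "A P value of <0.05 was considered statistically significant for all statistical tests". Neither section gives a control incidence, sidedness, a multiplicity rule, the number of time points or the within-patient correlation.

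**The concern.** Four groups of 50 make 200, but three arms of 50 make 150, and 200 over three arms is about 67 each. The text does not say which is meant, so the quoted detectable effects belong to a design other than the one listed.

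Two of the figures also raise questions of their own. A fixed difference in incidence cannot have one power value at all base rates, yet 26 points is given for categorical outcomes in general. And the two MAP translations use the same SD but do not appear to use the same conversion from f.

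This paragraph is where a reader would look to judge a non-significant result. If its figures describe another design, or hold only under unstated conditions, that judgement is unsound.

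**Working it through.** **Inputs from the documents.** Power 80%; alpha 0.05; N = 200; 50 per group; 26 points (read as absolute); f = 0.24 and 0.09; SD 10; 5 and 3 mmHg; three listed arms. **Assumed, because not stated.** Two-sided tests, pairwise comparison of two arms, no multiplicity adjustment.

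**1. Reproducing f = 0.24.** One-way ANOVA, noncentral F with k − 1 and N − k degrees of freedom and noncentrality f²N:

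| Groups | N | f at 80% power | Power at f = 0.24 |
|---|---|---|---|
| 4 | 200 | 0.236 | 81.5% |
| 3 | 200 | 0.221 | 86.4% |
| 3 | 150 | 0.256 | 74.3% |

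Only the four-group row rounds to the stated 0.24.

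**2. The 26-point difference.** With p̄ the mean of the two rates and n per arm (pooled-variance test):

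power = Φ{ [0.26√n − 1.96√(2p̄(1 − p̄))] / √[p₁(1 − p₁) + p₂(1 − p₂)] }

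For 37% vs 63% and n = 50: (0.26 × 7.071 − 1.96 × 0.7071) / √0.4662 = (1.8385 − 1.3859) / 0.6828 = 0.663, so power is 74.6%. Other pairs:

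| Rates | n = 50 | n = 67 |
|---|---|---|
| 5% vs 31% | 93.5% | 98.1% |
| 20% vs 46% | 79.9% | 90.2% |
| 30% vs 56% | 75.5% | 86.8% |
| 37% vs 63% (worst) | 74.6% | 86.2% |
| 50% vs 76% | 77.7% | 88.5% |
| 60% vs 86% | 84.4% | 93.3% |

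At n = 50, power is 80% or more when the lower rate is at most about 19.5% or at least about 54.5%. This holds whichever arm has the lower rate. Solving for the difference at 80% power over all base rates, the worst case is 27.7 points at n = 50. It is 24.2 points at 66 per arm and 24.0 at 67. For 26 points to have 80% power at the worst base rate, 57 per arm are needed.

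**3. The MAP figures.** The 5 mmHg follows from difference = 2 × f × SD (four groups, two high and two low): 2 × 0.24 × 10 = 4.8. The same formula for change gives 2 × 0.09 × 10 = 1.8, not 3.

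This does not depend on the pattern of means. With a common SD, any single multiplier that turns 0.24 into a value rounding to 5 (4.5 to 5.5) turns 0.09 into 4.5 × 0.09/0.24 = 1.7 to 5.5 × 0.09/0.24 = 2.1. To reach 2.5, which rounds to 3, the multiplier would make f = 0.24 equal 2.5 × 0.24/0.09 = 6.7.

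A separate conversion may have been used for change. If f = 0.09 is a group-by-time interaction with two time points and four groups, the most favourable pattern gives 4 × 0.09 × 10 = 3.6. That is not a lower bound for more time points. With three groups and three times, a cyclic pattern of interaction effects (0, −1, +1 and its rotations, scaled by √1.5 to unit root mean square) has a largest difference in change of 3 × √1.5 × 0.9 = 3.3, which rounds to 3.

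**The case against.** The strongest defence is that much of the paragraph stands. The f = 0.24 is right for four groups and N = 200. The 26 points reproduces at 20% vs 46% (79.9%) and is exceeded at lower or higher base rates. With a one-sided test at 0.05 it has at least 83.9% power throughout. If 200 patients go to three arms, both figures are conservative. Figure 1 may show how 3 mmHg was obtained. All of this is correct, and it limits the point to restating and reconciling.

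Three stronger readings are tempting, and the documents do not support them.

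- **A reader might infer that the trial cannot detect 26 points at 80% power.** That fails: it depends on the base rate, which is not given, and on whether the per-arm number is 50 or about 67. The abstract and background describe hypotension as common but give no incidence, so they do not place it in the range where power falls short.
- **A reader might infer that 3 mmHg is impossible or underpowered.** That is not shown. The number of time points, the correlation and the meaning of the SD are missing from the text, and some extreme patterns do give a value that rounds to 3.
- **A reader might infer that the shortfall is large because an exact test on two proportions would show less power.** The plan specifies logistic regression, so such figures do not describe the planned analysis.

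What the defence does not answer is the conflict over the number of arms, the absence of a base rate, and the mismatch between the two MAP conversions.

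**Conclusion.** The stated detectable effects are those of a four-group design that the protocol does not otherwise describe. For the three listed arms, f at 80% power is 0.221 with 200 patients, slightly better than stated. With 150 it is 0.256, slightly worse, and f = 0.24 then has 74% power.

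The 26-point figure is conditional on an unstated base rate. At 50 per arm it can be up to 1.7 points too optimistic (27.7 against 26), with power as low as about 75%. At about 67 per arm it is at least 1.8 points conservative even at the worst base rate (24.2 against 26, taking 66 per arm). These figures rest on two-sided, pairwise, unadjusted tests with no loss of patients, and on the pooled-variance test as an approximation to a two-arm logistic comparison. A dose trend or a multiplicity adjustment would change them.

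The 3 mmHg is inconsistent with the conversion behind 5 mmHg and cannot be verified from the text. It should be treated as unexplained, not as shown to be wrong. The discrepancies are modest, but the figures should be corrected because the trial's results will be read against them.

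**What to change.** 1. Reconcile the number of arms between the randomisation sentence, the list of groups and the sample-size paragraph, and state the total and per-arm number.
2. Restate the detectable effects for three arms, with an assumed control incidence and its source, the sidedness, and whether the comparison is pairwise or a dose trend. Under the assumptions above, the incidence figure is up to 28 points at 50 per arm (f = 0.256) or up to 24 points at about 67 per arm (f = 0.221).
3. Re-derive or correct the 3 mmHg. State the number of time points, the within-patient correlation, whether the SD of 10 is for a level or a change, and the conversion from f to mmHg. If Figure 1 already contains this, repeat it in the text.

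The cost is restated figures only, with no extra patients beyond the stated 200. If the intended design is 50 per arm in three arms, the restated figures become slightly less favourable.
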